opioid prescribing practices following Ob-Gyn surgery, we could not find any studies that reported opioid *consumption* following gynecologic or urogynecologic surgery. In order to perform the power calculations necessary for Specific Aim 2 (comparing opioid use between groups), because the actual number of opioids consumed following urogynecologic surgery is unknown, we will assume that patient-centered pre-operative education will result in a 33% decrease in narcotic consumption following hospital discharge compared to the control group. If we assume that controls consume a mean of fifteen 5 mg oxycodone pills (SD of +/-11 pills), and if we assume that the patient-centered group consumes 33% fewer pills (i.e. 10 pills in the modified education group), we would need a total of 152 participants (76 per group) to complete treatment and follow-up for a two-tailed t-test to have 80% power at $\alpha=0.05$. Assuming approximately 30% of patients will cancel surgery after randomization (including medical or insurance issues or change their mind) or will be lost to follow-up; we would need to enroll up to 198 women (99 per group) or until our designated power is met. We will perform between group comparisons using Chi-squared tests for categorical variables and t-tests for continuous variables. We anticipate that specific covariates (e.g. baseline questionnaire results, and narcotic use in last 3 months) may be confounders and that multivariable analyses will be required to evaluate the between group differences in outcomes. Note 1: When studies involve consent, an individual is considered a research subject once they have provided consent. If the research includes screening procedures after consent, please indicate the number of subjects that need to be recruited and the number that will actually participate in the research post-screening.

6. Study Timeline

Subjects in Aim 1 will participate in one focus group. Subjects in Aim 2 will participate up to the 6 week post-operative visit. This could occur within a window up of up to 8 weeks past their surgery.

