We will be able to complete this project within the planned timeframe outlined below. The UNM Urogynecology Division performed approximately 230 major pelvic floor operations last year (average of 19/month). We will create the database, standardize current pre-operative sessions, and prepare the manual of operations and focus group script for Specific Aim 1 over the next 3 months. We will identify patients for enrollment in the focus groups during this initial period. This preparation will then allow us to successfully execute specific Aim 1 over the subsequent 3 months. We will have biweekly to weekly focus group meetings during the start-up period of the grant cycle. This allows 8-10 weeks to review our findings and develop a patient-centered educational plan. We will then enroll up to 198 women or until our specified power is met over the next 1-4 years given the halt of all elective surgeries with the Covid pandemic(averaging 11 participants/month). We anticipate finishing recruitment by October 2021 and follow up for those randomized by December 2021. We, thus, expect to meet our recruitment goals. The last 3 months of the grant cycle will be dedicated to statistical analysis and abstract and manuscript preparation. As all patients receive pre-operative education and have scheduled 2 and 6-week post-operative visits, we anticipate that the vast majority of our patients will be

willing and able to participate in this study. Experience indicates that our patients have willingly participated in previous RCTs with high retention rates. We expect that this pattern will continue. We will continuously evaluate our recruitment numbers.

Timeline	March-May 2018	June-August 2018	Sept 2018-December 2021 (3 years, 3 months)	December 2021-February 2022
IRB submission, Database creation, Focus group recruitment planned, Standardize patient-centered pre-operative education	↔			
Conduct focus group sessions, Standardize patient-centered pre-operative education		↔↔		
Recruit & follow 180 patients until 6-weeks after surgery			↔↔	
Data analysis, manuscript preparation				↔↔

7. Study Endpoints

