All surgeries will take place at UNM Main, OSIS or SRMC operating rooms. Questionnaires and data collection will occur in the Urogynecology clinics at UNM or SRMC, by phone, HIPAA compliant Zoom or email link to REDCap, whichever is best for the participant. All data will be collected prospectively.

Participant Flow through the Study: Figure 1 (N range pending funding)

Randomized trial on expectations and pain control advancement in surgery: REPAIR

13. Data Analysis

Power Calculation & Statistical Analysis: Although few studies describe opioid prescribing practices following Ob-Gyn surgery, we could not find any studies that reported opioid *consumption* following gynecologic or urogynecologic surgery. In order to perform the power calculations necessary for Specific Aim 2 (comparing opioid use between groups), because the actual number of opioids consumed following urogynecologic surgery is unknown, we will assume that patient-centered pre-operative education will result in a 33% decrease in narcotic consumption compared to the control group. If we assume that controls consume a mean of fifteen 5 mg oxycodone pills (SD of +/-11 pills), and if we assume that the patient-centered group consumes 33% fewer pills (i.e. 10 pills in the modified education group), we would need a total of 152 participants (76 per group) to complete treatment and follow-up. Assuming approximately 30% of patients will cancel surgery after randomization or will be lost to follow-up; we would need to enroll 198 women (99 per group). We will perform between group comparisons using Chi-squared tests for categorical variables and t-tests for continuous variables. We anticipate that specific covariates (e.g. baseline questionnaire results, and narcotic use in last 3 months) may be confounders and that multivariable analyses will be required to evaluate the between group differences in outcomes.

14. Provisions to Monitor the Data to Ensure the Safety of Subjects

Subjects will participate in focus groups and then receive preoperative education and shared decision making on quantity of opioid prescribed postoperatively. Therefore the risks inherent to participation in the study are only minimal. As this is a minimal risk study, our Data Safety Monitoring Plan will entail the review of data monthly by staff and the PI or a mentoring co-investigator. We will assess for harm such as over treatment

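### The 30% loss allowance is applied as 152 × 1.30 instead of 152 / 0.70, so 198 randomised women are expected to yield about 138 completers and 75.5% power, not 152 and 80%

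*Combined protocol and SAP*

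**What the plan says.** The power paragraph in Section 5 (Number of Subjects) assumes that controls take a mean of 15 oxycodone pills with an SD of 11, and that the patient-centered group takes 10. From this it concludes that "we would need a total of 152 participants (76 per group) to complete treatment and follow-up", for a "two-tailed t-test to have 80% power" at a significance level of 0.05. It then assumes that about 30% of patients will cancel surgery after randomisation or be lost to follow-up, and states "we would need to enroll up to 198 women (99 per group) or until our designated power is met".

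Section 13 (Data Analysis) repeats the calculation without the closing clause: "Assuming approximately 30% of patients will cancel surgery after randomization or will be lost to follow-up; we would need to enroll 198 women". The opening of Section 5 separately caps recruitment to the randomised trial at 198. The text of Section 6 (Study Timeline) also gives 198 as an upper limit, but the table in the same section reads "Recruit & follow 180 patients until 6-weeks after surgery".

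**The concern.** The 30% is defined as a share of the women randomised. The number to randomise must therefore leave 152 after 30% of it has been removed, which means dividing 152 by 0.70. Adding 30% of 152 to 152 gives a smaller number, and 198 is that smaller number.

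The 80% power is the plan's justification for its size. If it does not follow from the plan's own assumptions, a null result would be reported as coming from an 80%-powered trial when the expected power was lower.

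Two further points in the wording add to this. The clause about enrolling until the designated power is met does not say what is counted. The 180 in the timeline table is a second, unexplained trial size.

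**Working it through.** **Inputs** (Section 5, power paragraph): difference 15 − 10 = 5 pills; SD 11; two-sided alpha 0.05; power 80%; equal allocation; loss 30% of those randomised; 198 enrolled.

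**1. Reproduce the 152.** By the normal approximation, n per group = 2 × (1.960 + 0.842)² × 11² / 5² = 75.98, so 76 per group and 152 in total. This matches the plan. The noncentral t solution is 76.95, so 77 per group; at 76 per group its power is 79.5%. The 152 is sound to within rounding.

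**2. Reproduce the 198.** 76 × 1.30 = 98.8, rounded up to 99 per group, 198 in total (152 × 1.30 = 197.6). Dividing does not give 198: 76 / 0.70 = 108.6, rounded up to 109 per group, 218 in total (152 / 0.70 = 217.1). So 198 came from multiplying by 1.30.

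**3. Expected completers from 198.** 198 × 0.70 = 138.6, about 69 per group and 13 to 14 women short of 152.

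**4. Loss that 198 can absorb.** 1 − 152/198 = 23.2%.

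**5. Power** (difference 5, SD 11, two-sided alpha 0.05):

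| Completers per group | Noncentral t | Normal approximation |
|---|---|---|
| 76 (planned) | 79.5% | 80.0% |
| 69 (198 less 30%) | 75.5% | 76.1% |

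The cost is about 4 percentage points on either basis. With 69 per group, the difference detectable with 80% power is 5.28 pills (5.28/15 = 35% of the control mean), against the planned 5 pills (33%).

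**6. Sensitivity to the loss rate**, 198 randomised, noncentral t with fractional group sizes (so the 30% row uses 69.3 per group, not 69):

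| Loss | Expected completers | Power |
|---|---|---|
| 20% | 158.4 | 81.1% |
| 25% | 148.5 | 78.6% |
| 30% | 138.6 | 75.7% |
| 35% | 128.7 | 72.5% |

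**7. Corrected target.** 218 × 0.70 = 152.6 completers, with 79.7% power by noncentral t, which is the planned level.

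**8. The 180 in the timeline table.** If it means women randomised, 180 × 0.70 = 126 completers, 63 per group, and power is 71.6%. If it means women followed to 6 weeks, that is 90 per group and power is about 86%. The table does not say which.

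**The case against.** **The power clause might rescue the figure.** Enrolling until the designated power is met could be read as continuing until 152 women complete. But in Sections 5 and 6 the clause is attached to an upper limit of 198, the opening of Section 5 sets that limit on its own, and Section 13 omits the clause. As written it permits stopping before 198, not going beyond it. At 30% loss, 198 is expected to be reached before 152 completers are. This is an expectation and not a certainty: with independent 30% losses, the chance of at least 152 completers from 198 is about 2%.

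**The loss might be lower.** The 30% is approximate, and Section 6 reports high retention in earlier trials. But 23% is not a rounding of 30%, and the 30% includes surgery cancelled for medical, insurance or personal reasons, which past retention does not address. If the sponsor expects less loss, the plan should say so.

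**The effect is small next to the uncertainty in the inputs.** This is true. The plan says that consumption after this surgery is unknown, so the mean and SD are assumptions. With 69 per group, an SD of 10.4 instead of 11 would restore 80%. So, roughly, would covariates explaining about 10% of the outcome variance, a figure assumed here and not given in the documents. Multivariable analyses are anticipated, but an adjusted model is not named as primary. These points limit the consequence; they do not make 198 the right inflation of 152.

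**Data-driven stopping is not planned.** Nothing in the documents describes looking at outcomes by arm to decide enrolment, and the clause most naturally means the 152 completers. It needs a definition, but it is not evidence of a problem in itself.

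**Conclusion.** The concern holds. On the plan's own inputs (difference 5 pills, SD 11, two-sided alpha 0.05, 30% loss after randomisation), 198 women are expected to give about 138 completers and 75.5% power. The plan's 152 completers have 79.5% by the same t-test calculation and 80.0% by the normal approximation. The 198 is adequate only for loss up to 23.2%.

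The error lies only in the attrition step. It costs about 4 points of power, does not bias the treatment estimate and does not raise the type I error rate. It still needs correcting, because the stated power, loss and enrolment cannot all be true together. The 180 is an inconsistency to reconcile; its effect on power depends on which reading was meant.

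**What to change.** Make Sections 5 and 13 agree with the arithmetic in one of these ways:

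- Keep 198 and 80%, and state that 198 allows for 23% cancellation or loss.
- Keep 198 and 30%, and state that about 138 completers give about 75% power for a 5-pill difference.
- Keep 80% and 30%, and raise the ceiling to 218 (109 per group) wherever 198 appears in Sections 5, 6 and 13.

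Replace the open-ended power clause in Sections 5 and 6 with a count, for example: enrolment continues until 152 women have a 2-week primary outcome, counted without reference to arm or outcome values, up to the stated maximum. With the maximum left at 198 this does not restore 80% power at 30% loss, so it must accompany one of the three changes above.

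In the Section 6 table, replace 180 with the enrolment ceiling, or say what 180 counts.

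The first two options cost wording only, and the stated loss or power becomes slightly less favourable. The third adds 20 women, a little under two months at the 11 per month given in Section 6 (20/11 = 1.8).

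### The enrolment cap of 198 does not deliver the stated 80% power at the plan's own 30% loss (it gives about 75.5%), and the timeline's 180 conflicts with it

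*Combined protocol and SAP*

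**What the plan says.** Section 5 (Number of Subjects) and Section 13 (Data Analysis) give the same calculation. It assumes that "controls consume a mean of fifteen 5 mg oxycodone pills (SD of +/-11 pills") and that "the patient-centered group consumes 33% fewer pills (i.e. 10 pills in the modified education group"). From this, Section 5 concludes that "we would need a total of 152 participants (76 per group) to complete treatment and follow-up" for 80% power with a two-sided t-test at 0.05. Both sections then allow for about 30% of women cancelling surgery after randomisation or being lost to follow-up.

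Enrolment is described in four ways:

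- Section 5, opening: up to 198 people for the randomised trial.
- Section 5, power calculation: "we would need to enroll up to 198 women (99 per group) or until our designated power is met".
- Section 6 (Study Timeline), text: "enroll up to 198 women or until our specified power is met".
- Section 13: a plain 198 (99 per group), with no power condition.

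The timeline table in Section 6 has a different number: "Recruit & follow 180 patients until 6-weeks after surgery".

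**The concern.** An allowance for loss should leave the required number of completers after the loss has occurred. Here the enrolment figure appears to be the completer number increased by 30%, which is not enough to withstand a 30% loss. If so, the stated 80% power and the 198 cap cannot both hold under the plan's own assumptions, and a trial run exactly to plan would finish smaller than the size it was justified on.

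Two wording problems add to this. The table's 180 leaves the reader unsure which total governs. The clause about power being met does not say how that is judged, so a later reader cannot confirm that the final size was fixed by count. At stake are the chance of detecting the assumed reduction in opioid use and an accurate statement of the planned size.

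**Working it through.** **Inputs.** From Sections 5 and 13: difference δ = 15 − 10 = 5 pills, SD σ = 11, loss 30%, 1:1 allocation. From Section 5: two-sided α = 0.05 and power 80%.

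**1. Reproduce the completer number.** Normal approximation:

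n per arm = 2σ²(z₀.₉₇₅ + z₀.₈₀)² / δ² = 2 × 121 × (1.960 + 0.842)² / 25 ≈ 75.98, so 76 per arm and 152 in total. The plan's figure reproduces. The exact t-test needs 77 per arm; at 76 its power is 79.5%, a trivial difference.

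**2. Reproduce the enrolment number.**

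- 152 × (1 + 0.30) = 197.6, rounded up to 198. This matches the plan.
- 152 / (1 − 0.30) = 217.1, rounded up to 218 (109 per arm). This does not match.

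The 198 therefore comes from multiplying by 1.3. Dividing by 0.7 is what leaves 152 after a 30% loss.

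**3. Completers and power at 30% loss** (δ = 5, σ = 11, two-sided 0.05):

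| Enrolled | Completers at 30% loss | Per arm | Power, exact t | Power, normal approximation |
|---|---|---|---|---|
| 198 | 198 × 0.7 = 138.6, about 138 | 69 | 75.5% | 76.1% |
| 180 | 180 × 0.7 = 126 | 63 | 71.6% | 72.3% |
| 218 | 218 × 0.7 = 152.6, about 152 | 76 | 79.5% | 80.0% |

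**4. Loss that each total can absorb and still give 152 completers.**

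- 198: 1 − 152/198 = 23.2%.
- 180: 1 − 152/180 = 15.6%.

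Neither reaches 30%. No stated input leads to 180.

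**5. Consequence for the stopping clause.** At 30% loss, 198 enrolled yields about 138 outcomes, which is short of 152. If the clause means stopping once 152 women have completed, it would not come into play under the plan's own assumptions, because the cap would end enrolment first.

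**The case against.** **The cap may never bind at 30% loss.** The plan says approximately 30%, and Section 6 reports high retention in earlier trials. If loss is 23% or less, 198 is enough. That is true, but 30% is the figure the plan uses to justify 198, and the power is stated without condition.

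**The clause might allow enrolment past 198.** Read that way, the shortfall would disappear. But Section 5 opens with a flat maximum of 198 and Section 13 gives 198 without qualification, so 198 reads as a ceiling.

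**The 180 is one table cell.** This stands. The text consistently says 198, nothing suggests that the table governs, and 180 does not breach a maximum. It needs reconciling, no more.

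**The stronger reading.** A reader might infer that stopping when power is met permits stopping on accumulating results, especially as Section 14 provides for "the review of data monthly by staff and the PI" or a mentoring co-investigator. The documents do not support that reading:

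- The sentence just before the Section 5 clause equates 80% power with 152 completers, so designated power most naturally means that count.
- Section 6 says that recruitment numbers are what will be evaluated continuously, and it places statistical analysis after follow-up.
- Section 14 presents the monthly review as safety monitoring, looking for adverse events, serious adverse events and reportable new information.
- No text mentions stopping on significance.

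Even if power were judged from observed data, simulations under no effect, with look schedules that had to be assumed because the plan contains none, gave type I error of about 5% to 7%. What remains is that no sentence says the judgement is by count, or rules out a comparison between arms before enrolment ends.

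**Conclusion.** The point holds as a numerical inconsistency. At the plan's own 30% loss, the cap of 198 gives about 138 completers and about 75.5% power, against a stated 80%: a shortfall of about 14 completers (152 − 138) and 4.5 percentage points. The table's 180 would leave 126 completers and about 72% power.

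These figures rest on the plan's assumed difference of 5 pills and SD of 11, on equal loss in the two arms, on everyone enrolled being randomised, and on lost women contributing no primary outcome. The plan itself calls actual consumption unknown, so true power could differ either way. The mismatch between 198, 30% and 80% follows from the stated inputs regardless.

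The plan does not describe outcome-driven stopping, and no claim of an inflated type I error is made here. The stopping clause needs clarifying only so that the likely intent is on the page.

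**What to change.** 1. **Sections 5 and 13.** State that 198 enrolled gives about 138 completers and about 75.5% power at 30% loss, and that 152 completers (80% power) requires loss of no more than about 23%. If the sponsor would rather keep 80% power at 30% loss, the arithmetic gives 218 enrolled, which is 20 more women. That is a choice for the sponsor and is not needed for consistency.
2. **Section 6 table.** Reconcile 180 with 198.
3. **Sections 5 and 6, stopping clause.** Replace the reference to power being met with: *or until 152 randomised women have a 2-week opioid outcome, judged by count without comparing outcomes between arms; all women already randomised at that point are still followed and analysed.* The last part matters because randomisation takes place at the pre-operative visit, so some women will still be awaiting surgery or follow-up when the 152nd outcome arrives.

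The cost is wording in three sections and one table cell, plus a less favourable stated power. No extra patients, visits or procedures are needed.

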The University of New Mexico (UNM) urogynecology division operates at two main locations. UNMH Women's Care Clinic located in northeast Albuquerque provides a full

Randomized trial on expectations and pain control advancement in surgery: REPAIR

range of services for women with pelvic floor disorders. The clinic consists of eight exam rooms and two treatment rooms. Our second location is at Sandoval Regional Medical Center (SRMC), a community based facility located in Rio Rancho, New Mexico, a large suburb located outside of Albuquerque.

Research Experience: The Urogynecology Division at UNM has a strong history of conducting high quality research and collaboration with other investigators in the US and abroad and has consistently met or exceeded recruitment goals on time. We were members of the NICHD-sponsored PFDN in the last grant cycle, and have met recruitment goals with high rates of follow-up and accurate data collection.

Our group is well versed in the importance of adherence to protocols, timely completion of regulatory requirements, effective recruitment strategies, and the importance of the inclusion of minority subjects. Research is integral to all aspects of Divisional work; importantly, all members of the clinical team participate in research efforts. There are weekly research meetings to discuss the progress of the ongoing studies within the department, and it is an excellent forum to ensure that all involved are adequately informed of their duties, of the protocol, and of the procedures.

We do not anticipate that emergency care will be needed for this study, however the urogynecology physicians are available on a 24-hour basis, 7 days per week for their patients requiring emergency care.

10. Prior Approvals

There will not be any approvals obtained prior to commencing the research. The study was presented for approval by the Department Chair or Vice Chair of Research. The signed Departmental Review form can be found in the “supporting documents”.

This study does not include any ionizing radiation, biologic specimens, or drugs. Medications prescribed to participants will be part of their standard of care.

11. Multi-Site Research

N/A this is not a multi-site study or a FDA regulated trial.

[figure not shown]
12. Study Procedures

The only procedures subjects will undergo are those that are needed as part of their routine preoperative, intraoperative and postoperative care. There are no procedures related to the study.

All surgeries will take place at UNM Main, OSIS or SRMC operating rooms. Questionnaires and data collection will occur in the Urogynecology clinics at UNM or SRMC, by phone, HIPAA compliant Zoom or email link to REDCap, whichever is best for the participant. All data will be collected prospectively.

Participant Flow through the Study: Figure 1 (N range pending funding)

Randomized trial on expectations and pain control advancement in surgery: REPAIR

13. Data Analysis

Power Calculation & Statistical Analysis: Although few studies describe opioid prescribing practices following Ob-Gyn surgery, we could not find any studies that reported opioid *consumption* following gynecologic or urogynecologic surgery. In order to perform the power calculations necessary for Specific Aim 2 (comparing opioid use between groups), because the actual number of opioids consumed following urogynecologic surgery is unknown, we will assume that patient-centered pre-operative education will result in a 33% decrease in narcotic consumption compared to the control group. If we assume that controls consume a mean of fifteen 5 mg oxycodone pills (SD of +/-11 pills), and if we assume that the patient-centered group consumes 33% fewer pills (i.e. 10 pills in the modified education group), we would need a total of 152 participants (76 per group) to complete treatment and follow-up. Assuming approximately 30% of patients will cancel surgery after randomization or will be lost to follow-up; we would need to enroll 198 women (99 per group). We will perform between group comparisons using Chi-squared tests for categorical variables and t-tests for continuous variables. We anticipate that specific covariates (e.g. baseline questionnaire results, and narcotic use in last 3 months) may be confounders and that multivariable analyses will be required to evaluate the between group differences in outcomes.

14. Provisions to Monitor the Data to Ensure the Safety of Subjects

Subjects will participate in focus groups and then receive preoperative education and shared decision making on quantity of opioid prescribed postoperatively. Therefore the risks inherent to participation in the study are only minimal. As this is a minimal risk study, our Data Safety Monitoring Plan will entail the review of data monthly by staff and the PI or a mentoring co-investigator. We will assess for harm such as over treatment

of pain, which is highly unlikely as we are complying with our standard of care. It would be unlikely that the study would require suspension as patients in the intervention arm are actually having less exposure to harm than the standard of care arm. Specific findings we will be looking for are adverse events, serious adverse events and reportable new information.

15. Withdrawal of Subjects

Any participant may withdraw from the study at any time without penalty and will continue to receive the clinical standard of care. A subject may be withdrawn from the study without her consent at the discretion of the physician and study staff if they believe she no longer meets study inclusion criteria or if she meets exclusion criteria, or if they believe that it is not in her best interest to continue study participation. Investigators may withdraw a subject if the subject is not following the study protocol. If a woman is withdrawn from the study either at her own discretion or that of the research staff, she may continue with the planned surgical procedure performed in the usual fashion.

To minimize withdrawal from the study, patients will be randomized at their pre-operative visit. According to the 2010 CONSORT guidelines, we will analyze all participants assessed for eligibility within the study. We will document reasons for withdrawal from the study including failure to meet eligibility criteria or participant declining enrollment into the study. We will report eligibility criteria not met or reasons for declining participation in the study. The withdrawal procedure is clearly documented in the study consent.

16. Data Management/Confidentiality

Randomization assignment will be generated by a computer based randomization table and assigned by a research coordinator. Assignments will be kept in sealed opaque envelopes numbered sequentially, and on the day of the patient's pre-operative visit, the surgeon will call a research coordinator who will open the next envelope in the sequence. All data collection sheets and questionnaires will contain the subject number and day of the clinic visit or day of completion. No other patient identifiers will be collected. PHI including patient name, date of birth, phone number, and medical record number will need to be collected to track for appointments.

The data collection, HIPAA and consent forms will be maintained in a locked file cabinet in the OBGYN administrative area. A separate folder will be designated for each participant. The offices have the additional security of being badge-access only for OBGYN department employees. A key matching study number to subject's name will be in a spreadsheet secured on a password protected computer.

The only PHI collected will be patient name, date of birth, medical record number and telephone number for site use only and to ensure patient follow up. This will not be entered into the database, but it will be kept with the other identifying information.

The data does not include sensitive information or information requiring additional protection.

Electronic data entry will be performed in the OBGYN administrative offices, using the de-identified subject study number. The electronic data will be encrypted, password protected, and stored on the secure UNM OBGYN department server. This server's electronic security is monitored / maintained by the Health Sciences Library and Informatics Center (HSLIC). A REDCap database will be created to collect, store and manage the data. REDCap databases are reposed securely. The REDCap database is only accessible using a individual unique login and password and access is only provided to co-investigators. Access is restricted to co-investigators and will be protected using the unique REDCap login and password provided to each co-investigator.

Access to the files and REDCap will be restricted to research personnel and Investigators and will be locked or protected using the unique REDCap login and password provided to each co-investigator. The data will be stored for 5 years after completion of analysis and then will be destroyed.

A Certificate of Confidentiality will not be used to protect data from forced release. No data will be transported to outside locations or shared with external institutions. Focus groups will be audio-recorded; the transcriptions will be de-identified and the original audio-recordings will be destroyed following manuscript publication. There will be no video recordings or photographs taken.

17. Data and Specimen Banking

As stated above, the data collection, HIPAA and consent forms will be maintained in a locked file cabinet in the OBGYN administrative area. A separate folder will be designated for each participant. A key matching study number to subject's name will be stored on a password protected computer on a secure UNM OBGYN department server. In order to further ensure patient confidentiality, the identifying information will be kept separately from the numbered study files in a locked cabinet. The data will be maintained for 5 years after completion of the study and then destroyed.

No specimens will be archived for future use. Additionally, this is neither a multi-center study nor will any information be banked or archived elsewhere.

18. Risks to Subjects

Focus groups by their nature cannot be anonymous. However, participants will be asked to keep what was discussed in the focus groups confidential and will be asked to use their first names only. The focus group transcripts will be de-identified. Risks of enrollment in the study include the risk of breach of confidentiality. We will take every measure to try to ensure the security and confidentiality of participants. This may result in stigmatization or hardship. Participants will be recruited in a private room and will have ample time to consider whether they want to participate in the study. Also, locked filing cabinets will be used to protect patient consent information and collected data. The link identifying patients and their study numbers will be also be stored on a password protected computer on a secure UNM OBGYN department server. There are risks of stress, emotional distress, and inconvenience.

Pregnant women will not be included in the study, so there is no risk to embryos/fetuses.

19. Potential Benefits to Subjects

Participation in this study may provide information that may help other people who have a similar medical problem in the future.

20. Recruitment Methods

We will recruit women from our urogynecology clinical practice at UNM and SRMC.

The urogynecology clinics at UNM and SRMC have a large referral population of patients who undergo pelvic floor surgery. Participants will be identified in the clinics at UNM/HSC and Sandoval Regional Medical Center by investigators. All patients scheduled for surgery will be approached for recruitment for the RCT portion of this study. The focus group participants will be identified through previous study consents that said they would be willing to be contacted for future research. Additionally, the urogynecology division keeps a computer record of the patients that had urogynecologic surgery over the past year as part of our standard care and scheduling. These patients may also be contacted by their surgeon to see if they are interested in participating in a focus group. Subjects are encouraged to consult with family, friends, and primary health care providers, as well as communicate any questions they may have before beginning the consent process.

If a woman is withdrawn from the study either by her desire or that of the research staff, or does not desire to participate, she will be offered the same treatment options.

There will be no other additional materials to recruit subjects.

21. Provisions to Protect the Privacy Interests of Subjects

Focus groups by their nature cannot be anonymous. However, participants will be asked to keep what was discussed in the focus groups confidential and will be asked to use their first names only. The focus group transcripts will be de-identified.

Privacy concerns are taken into account with every patient seen at the UNM and SRMC. Participants approached and/or interviewed in the clinic setting will be in private offices or examination rooms in the UNM or SRMC clinic, where all staff, including research staff, are well-versed in sensitive health care discussions and procedures. Telephone interviews for recruitment and study data gathering are conducted in the research staff area or private physician offices, where all staff have received CITI Training. The office area designated for the entire urogynecology research staff is isolated from the clinical administrative staff area, providing protection for participants and potential participants during screening, recruitment, study-designated calls, and data entry.

All study sheets used to collect patient information will be de-identified.

Randomized trial on expectations and pain control advancement in surgery: REPAIR

At all times throughout the clinical investigation confidentiality will be observed by all parties involved. All data will be secured against unauthorized access. Privacy and confidentiality of information about each subject will be preserved in study reports and in any publication. Each subject participating in this study will be assigned a unique identifier. HIPAA authorization is within the consent. All documents containing personal health information (screening logs, consent documents, data forms) are maintained in locked file cabinets with access available only to research staff and investigators. Data is entered into a password-protected system. No individual identifiers are entered into the system. The sole link with personal information is maintained by the research team on a password protected computer on a secure UNM OBGYN department server with access limited to authorized research staff and investigators. This information is only to be used at the study center.

22. Economic Burden to Subjects

Research Procedures	Number of Samples/Procedures	Responsible Party	
		Study	3 rd Party Payer or Participant
Focus Group – Aim 1	1		
Demographic Form	1		
PROMIS Physical Function SF	3		
PROMIS Pain Interference SF	3		
Patient Satisfaction and Preparedness for Surgery Questionnaire	1		
Medication Diaries	2		
Opioid History			
			
Standard of Care Procedures	Number of Samples/Procedures	Responsible Party	
		Study	3 rd Party Payer or Participant
Urogynecology Clinic Visits pre-op, 2 & 6 week post-op	3		
Pelvic Floor Surgery	1		
Pain medication post-op	Varies per patient		
			
			
			
			
			

23. Compensation

Pending funding - For enrollment in Aim 1, participants will receive a \$50 merchandise card for their participation in one focus group. For enrollment in Aim 2, participants will receive a \$10 at their initial visit, \$20 at their 2-week post-operative visit and \$20 at their 6-week post-operative visit for a total of \$50 in merchandise cards for their participation in the study. This incentive will offset the cost of subject's time and transportation while participating in the study.

24. Compensation for Research-Related Injury

If participants are injured or become sick as a result of this study, UNM HSC or SRMC will provide emergency treatment at the study participant's cost. No commitment is made by the University of New Mexico Health Sciences Center to provide free medical care or money for injuries to participants of the study. Reimbursement for treatment for all related costs of care will be sought from the participant insurer, managed care plan, or other benefits program. The participant will be responsible for any associated co-payments or deductibles required by the insurance. Participants will be asked to report any illness or injury they believe to be related to the study to the investigator or research staff. Participants will be given telephone contact information for the urogynecology office for the purpose of asking any questions or stating any concerns about the study or treatment as a research subject. They may also be directed toward the HRPO. This language will be stated in the consent document and reviewed during the informed consent process. There is no additional risk to participate in this study.

25. Consent Process

Patients will be approached about the research study at the urogynecology clinics at UNM and SRMC, as well as on phone and by HIPAA compliant Zoom, after the patient has decided to have surgery. The study consent will be obtained by one of the research team members. Verbal consent will be noted on the updated consent form with a space to also sign if the patient has an office visit in person. Due to the pandemic, research coordinators are mainly working from home and going through the consent with participants by phone for the safety of everyone. Privacy is still maintained as the coordinator ensures they have a place they can talk privately by phone. Additionally, care will not be withheld if they decide not to participate.

